3.1 Overall Design

This is an open-label, long-term multicenter, study to evaluate the safety and efficacy of topical tapinarof cream, 1% in subjects with AD. Subjects in this study will have either: a) completed treatment with tapinarof or vehicle in one of two Phase 3 pivotal safety and efficacy studies, DMVT-505-3101 or DMVT-505-3102, and rolled over into this study; b) completed treatment with tapinarof in the Phase 2 maximal use PK study, DMVT-505-2104, and rolled over into this study; or c) enrolled directly into this study. This study will consist of up to 48 weeks of treatment and a 1-week safety follow-up period.

At the completion of the Week 8 visit of study DMVT-505-3101 or study DMVT-505-3102 or the Day 28 visit of study DMVT-505-2104 (Baseline [Day 1] in this study), all eligible subjects will be offered enrollment in this OL-LTE study. Approximately 125 additional pediatric subjects ages 2 to < 18 years who are not eligible for participation in the Phase 3 pivotal studies (DMVT-505-3101 or DMVT-505-3102) will be enrolled directly into this OL-LTE study. Study visits during the treatment period for all subjects will occur every 4 weeks (\pm 3 days). Unscheduled visits may occur, as needed. Subjects who withdraw from the study before Week 48 will return to the study site for an Early Termination visit. The total duration of subject participation in this study will be approximately 49 weeks for rollover subjects (Baseline to Follow-Up) and approximately 53 weeks for direct-enrolling subjects (Screening to Follow-Up).

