6.2 Safety Assessments

6.2.1 Adverse Events

All AEs and SAEs will be collected from the time the subject signs the informed consent form (ICF) until the final visit/contact with the subject. AEs that began during the parent study and were ongoing at the end of that study will be reported as ongoing AEs. Additional safety information, including the definition of an AE and the methods for recording, evaluating, and assessing causality of AEs and the procedures for completing and transmitting SAE reports are provided in [Section 8](#).

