13.2 Adverse Events

All AE summaries will be restricted to TEAEs. For rollover subjects, all AEs reported in this study will be considered as TEAEs except for those AEs resolved prior to the Visit 1 date in this study. For direct-enrolling subjects, all AEs that start after the first dose of study drug will be

considered a TEAE. Verbatim terms in the eCRFs will be mapped to PTs and SOCs using MedDRA, Version 24.0.

Imputation of start and end dates of AEs

To calculate duration of AEs, the following rules will be used where applicable to impute partial or completely missing start dates or end dates:

- If only the day is missing for a start date, the 1st of the month will be imputed. If the new estimated date falls before the Visit 1 date, while the known month and year match the month and year of the Visit 1 date, the date of Visit 1 will be used as the new estimated date.
- If only the day is missing for an end date, the last day of the month will be imputed. If the new estimated date falls after the date of last study visit, the date of last study visit will be used as the new estimated date.
- If both the day and the month are missing for a start date or end date, no imputation will be used, and the duration will not be calculated.
- If the start date or end date is completely missing, duration will not be calculated.

For AEs ongoing at the end of the previous studies, duration will be computed using the DMVT-505-3103 Visit 1 date as the AE start date.

Imputation of missing relationship and/or missing severity

If relationship to treatment is missing, the event will be conservatively treated as related to study drug.

If severity is missing and the AE is reported as serious and fatal, severity will be imputed as CTCAE=5. If severity is missing and the AE is reported as serious and not fatal, severity will be imputed as CTCAE=4. If severity is missing and the AE is not reported as serious, severity will be imputed as CTCAE=3.

All TEAEs will be listed by subject, detailing the verbatim term given by the investigator, PT, SOC, onset date, end date, ongoing at the end of parent studies (Y/N), duration (days), CTCAE grade, outcome, relationship to study drug, action taken with study drug, other action taken to treat the event, AE of special interest (AESI) (Y/N), seriousness and criteria for seriousness.

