AEs resolved prior to the Visit 1 date, Serious TEAEs, TEAEs leading to study drug discontinuation, TEAEs leading to study discontinuation and TEAEs related to study drug will also be listed separately. The following AESIs will be identified and listed separately: contact dermatitis, follicular event, and headache.

The frequency and percent of subjects with AEs will be summarized as incidence rates of:

- Any AE

The frequency and percent of subjects with TEAEs will be summarized as incidence rates of:

- Any TEAE
- Any TEAE excluding those ongoing at the end of the previous studies
- Any TEAE ongoing at the end of the previous studies
- Any treatment-emergent AESIs
- Any treatment-emergent AESIs excluding those ongoing at the end of the previous studies
- Any treatment-emergent AESIs ongoing at the end of the previous studies
- Any treatment-related TEAE
- Any TEAE leading to study drug discontinuation
- Any TEAE leading to study discontinuation
- Any serious TEAE
- Death
- Treatment-related serious TEAE
- Serious TEAE leading to study drug discontinuation
- Serious TEAE leading to study discontinuation
- TEAE (COVID-19)

TEAEs will be sorted alphabetically by SOC and decreasing PT frequency in the Total (Overall) group for the following:

- All TEAEs
- All TEAEs by maximum CTCAE grade

- All TEAEs by maximum causality (not related, related) to the study drug
- All TEAEs excluding those ongoing at the end of the previous studies
- All TEAEs ongoing at the end of the previous studies
- All treatment-related TEAEs
- All TEAEs leading to study discontinuation
- All TEAEs leading to study drug discontinuation
- All serious TEAEs
- All serious TEAEs leading to study discontinuation
- All serious TEAEs leading to study drug discontinuation

All TEAEs and all serious TEAEs will also be summarized by SOC (alphabetical order) and PT (descending order) for the following subgroups:

- Age (2-6 yrs, 7-11 yrs, 12-17 yrs, ≥ 18 yrs)
- Sex
- Race (White, Asian, Black or African American and Other)

TEAEs by maximum CTCAE grade, TEAEs by maximum causality, TEAEs leading to study drug discontinuation and TEAEs leading to study discontinuation, will be summarized by SOC (alphabetical order) and PT (descending order) for the Age subgroup.

Furthermore, TEAEs will be categorized by day of onset among the following 4 categories:

- ≤ 12 weeks
- > 12 to ≤ 24 weeks
- > 24 to ≤ 48 weeks
- > 48 weeks.

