For each of these categories, TEAEs will be summarized by SOC in alphabetical order and PT in descending order of frequency. TEAEs ongoing at the end of the previous studies will be considered in the first category (i.e., day of onset ≤ 12 weeks).

At each level of summarization, a subject will be counted once if he/she reported one or more events. The severity of TEAEs and relationship to study drug will be summarized in a similar manner. For summaries of relationship to study drug, a subject will be classified according to related or not related. For summaries of TEAE CTCAE grade, a subject will be classified according to the worst grade.

For treatment-emergent AESIs, summarization will be more extensive, reflecting the more detailed information collected. Information summarized will include number of events per subject, earliest onset day, duration (in days), causality, grade and seriousness of AESIs, outcome, actions taken, assorted physical characteristics of the AESIs, and demographic/baseline characteristics and vIGA-AD™ status of the subjects experiencing them. Each type of AESI will be summarized separately. If a subject has more than one treatment-emergent occurrence of an AESI, the subject's maximum duration, highest levels of causality and seriousness, maximum grade and generally the most extreme level of each characteristic will be summarized. If an AESI was ongoing at end of study (EOS), it will not be included in the duration summary. AESIs ongoing at the end of previous studies will also be included in the summary.

A Kaplan-Meier figure will be generated for each AESI of time to first event for events starting during the study. Time to first onset will be computed as Onset Date of First Occurrence – Date of Visit 1 + 1 if onset date is on or after visit 1 date. Otherwise, time to first onset will be computed as Onset Date of First Occurrence – Date of Visit 1. Subjects not experiencing the AESI will be censored at the date of study completion or discontinuation. AESIs ongoing at the end of the previous studies will not be included.

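### The day-of-onset TEAE table in SAP 13.2 puts events that began before Visit 1 into its first 12-week category, and no version of that table leaves them out

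*SAP*

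**What the plan says.** SAP 13.2 (Adverse Events) plans a SOC/PT summary of TEAEs by day of onset in four categories: up to 12 weeks, over 12 to 24, over 24 to 48, and over 48 weeks. It then states that "TEAEs ongoing at the end of the previous studies will be considered in the first category". SAP 7 counts study days from Visit 1 of the extension.

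The events concerned are described in Protocol 6.2.1: "AEs that began during the parent study and were ongoing at the end of that study will be reported as ongoing AEs". For rollover subjects, Protocol 10.4.3 and SAP 13.2 both treat such an event as a TEAE unless it resolved before Visit 1. For direct-enrolling subjects a TEAE must start after the first dose.

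Elsewhere in SAP 13.2 the carried-over events are kept apart:

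- The overview has any-TEAE and any-AESI rows with, without and only the carried-over events.
- Two SOC/PT tables are planned, "All TEAEs excluding those ongoing at the end of the previous studies" and "All TEAEs ongoing at the end of the previous studies", each over the whole study.
- For the AESI time-to-first-event figures, "AESIs ongoing at the end of the previous studies will not be included".
- The TEAE listing shows the onset date and a yes/no flag for events carried over from a parent study.

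**The concern.** An onset table has one job: to show when events began. Carried-over events began before Day 1, yet they are counted as onsets in the first 12 weeks of the extension. No second version of the table omits them, although the SAP makes that separation in its other main TEAE displays.

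Safety is the first objective, and this is the only planned summary of onset timing across all SOCs and PTs, since the Kaplan-Meier figures cover AESIs only. A reader who compares the first category with the equally long second one could see an early cluster of events that then subsides, when part of the cluster is parent-study carry-over. A comparison of rollover and Direct-Enroll columns in the first category is affected in the same way. SAP 10.5 has all summaries produced at the interim, so the effect would appear there too.

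**Working it through.** **Text check.** The plan states no figure for this table, so there is none to reproduce. Put side by side: Protocol 6.2.1 places the start of these events in the parent study, SAP 7 starts the clock at Visit 1, and SAP 13.2 assigns the events to the first post-Visit-1 category. The visible SAP text plans no onset table without them. Table shells were not available.

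**Direction and reach.** Adding events to a count of subjects cannot lower it. Direct-enrolling subjects have no carried-over TEAEs. The rule therefore affects only the rollover columns and the totals that include them: up to 836 of 836 + 125 = 961 subjects, or 87.0% (SAP 5).

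**Illustrative size.** All rates here are assumptions:

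- p = share of subjects with a new-onset TEAE per 12 weeks (10%, 15%, 20%), constant over time, no dropout
- c = share of rollover subjects with a carried-over TEAE, independent of new onset
- 8 parent-study weeks for every rollover

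Protocol 3.1 sets rollover "At the completion of the Week 8 visit of study DMVT-505-3101 or study DMVT-505-3102 or the Day 28 visit of study DMVT-505-2104", so 8 weeks overstates carry-over for the DMVT-505-2104 subjects.

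First-category count: F = 836 × [1 − (1 − p)(1 − c)] + 125 × p. Expected second-category count: 961 × p. Hence ratio = F / (961p) = 1 + (836/961) × c(1 − p)/p. Without carry-over it is 1.

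Three ways to set c:

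- a nominal 2%
- AEs resolving with mean duration d weeks: c = 1 − exp[−h·d·(1 − exp(−8/d))], with h = −ln(1 − p)/12
- a ceiling at which no parent-study AE ever resolves: c = 1 − (1 − p)^(8/12)

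| p | c = 2% | d = 2 | d = 4 | d = 8 | Ceiling |
|---|---|---|---|---|---|
| 10% | 1.157 | 1.134 (c 1.7%) | 1.234 (c 3.0%) | 1.340 (c 4.3%) | 1.531 (c 6.8%) |
| 15% | 1.099 | 1.129 (c 2.6%) | 1.226 (c 4.6%) | 1.326 (c 6.6%) | 1.506 (c 10.3%) |
| 20% | 1.070 | 1.125 (c 3.6%) | 1.217 (c 6.2%) | 1.312 (c 9.0%) | 1.481 (c 13.8%) |

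**Can other planned tables recover the right count?** Within each level, "a subject will be counted once if he/she reported one or more events", and one subject may have both a carried-over and a new event. If C = 836c subjects appear in the carried-over table, new onsets in the first category lie between F − C and F. Under independence the simple subtraction F − C falls short of the expected count by the overlap, 836 × c × p:

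| p | c | F | C | F − C | Expected new onsets (961p) | Shortfall |
|---|---|---|---|---|---|---|
| 10% | 2% | 111.1 | 16.7 | 94.4 | 96.1 | 1.7 |
| 10% | 6.8% (ceiling) | 147.1 | 56.7 | 90.4 | 96.1 | 5.7 |
| 20% | 13.8% (ceiling) | 284.6 | 115.6 | 169.1 | 192.2 | 23.1 |

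For a single PT with an assumed 1% risk and its ceiling of 0.67%, the overlap is 836 × 0.01 × 0.0067 ≈ 0.06 subjects. Subtraction is therefore not exact, but usually close. The table that excludes carried-over events pools all periods, so it does not give the first-category count. The listing would give it exactly, by hand.

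**The case against.** The strongest reply is that this is a disclosed convention. SAP 13.2 states the rule openly, and it fits the neighbouring rule that uses the Visit 1 date as the start of a carried-over AE when duration is computed. The first category has no lower bound, and SAP 7 gives dates before Visit 1 negative study days, so such events formally satisfy it. Carried-over events are tabulated and flagged elsewhere, the AESI figures are clean, and nothing is tested.

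Most of this stands. There is no internal contradiction and no loss of data. The duration rule does not rescue the onset table, though. Counting duration from Visit 1 measures time within this study, whereas an onset category says when the event began. A reader will take the first category as a 12-week period, comparable with the next.

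The size is also open to challenge. Every rate is assumed, and a ratio near 1.5 needs no parent-study AE ever to resolve. The model ignores selection: rollovers had to be completers still on study drug, without a related SAE or an AE that ended treatment. Treatment is intermittent, so constant risk is only a reference point. These objections limit the magnitude and leave the direction unchanged.

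A reader might also infer more than the documents support:

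- That the SAP never separates carried-over AEs. It does, in the overview, the all-period tables, the listing and the AESI figures.
- That the TEAE definition is wrong. It agrees with Protocol 10.4.3.
- That the new-onset count is lost. Subtraction comes close and the listing gives it exactly.
- That the table hides its denominator. SAP 6 has footnotes state the percent basis, and SAP 9.1 summarises time in study with a Kaplan-Meier figure.

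**Conclusion.** The point holds as a modest bias in one descriptive table. By its own rule, the onset table counts pre-Visit-1 events as first-12-week onsets. It can only raise that category, for rollover groups and the totals that include them. The first category is then not comparable with later categories or with the Direct-Enroll column.

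The size cannot be known from the documents. Under the stated assumptions the first-to-second ratio would be about 1.12 to 1.34 if AEs resolve with a mean duration of 2 to 8 weeks. The wider range, from 2% carry-over to the ceilings, is 1.07 to 1.53, and its upper end is an extreme case. No TEAE total, test or decision rule is affected. The change is worth making because the set it needs is already defined in the SAP.

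**What to change.** In SAP 13.2, produce the day-of-onset SOC/PT table on TEAEs excluding those carried over from the parent studies. Add a footnote pointing to the planned table "All TEAEs ongoing at the end of the previous studies", or give one summary count labelled as onset before Visit 1. A full SOC/PT block for that extra category is unnecessary, since it would repeat the planned table. Apply the same rule at the interim and final analyses. Leave the TEAE definition and all other tables unchanged.

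The cost is a sentence in the SAP, a filter on an existing flag and a footnote, with no new data. First-category percentages will fall somewhat. Showing how many subjects remain in the study at the start of each category would help with the unequal widths, but is optional.

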14. A history of or ongoing serious illness or medical, physical, or psychiatric condition(s) that, in the Investigator's opinion, may interfere with the subject's participation in the study, interpretation of results, safety of the subject or ability to understand and give informed consent.
15. Known hypersensitivity to tapinarof or excipients.

Investigational Product, Dosage and Mode of Administration:

Tapinarof cream, 1% is a white to off-white cream containing 1% weight/weight (10 mg/gram) tapinarof, supplied in 30-gram tubes, and is to be administered by the subject or their caregiver OD via topical application of a thin layer to affected areas.

Reference Therapy, Dosage and Mode of Administration:

Not applicable.

Duration of Treatment:

Subjects enrolling in this study may receive treatment for up to 48 weeks. The duration of treatment is based on the vIGA-AD™ score. The end of the study is defined as when the last active subject has completed the Follow-up Visit.

Criteria for Evaluation:

Criteria for Evaluation:	
Efficacy Assessments:	
 • vIGA-AD™ • Eczema Area Severity Index (EASI) • Percentage of total body surface area (%BSA) affected
Functional Outcomes and Quality of Life Assessments:	
 • PP-NRS, for completion by subjects ages \geq 12 years and for completion by caregivers of subjects ages < 12 years • [REDACTED] • [REDACTED] • [REDACTED] • [REDACTED]
Safety Assessments:	
 • AEs • Vital signs • Physical examinations • Clinical laboratory tests • [REDACTED]
Study Endpoints:	
 • Incidence, frequency, and duration of treatment-emergent AEs and SAEs • Change from Baseline in laboratory values • Change from Baseline in vital signs • [REDACTED] • [REDACTED] • [REDACTED] 
 ○ [REDACTED] ○ [REDACTED] ○ [REDACTED] • [REDACTED] 
 ○ Proportion of subjects who achieve vIGA-AD™ = 0 at least 1 time during the study ○ [REDACTED]

- For subjects entering the study with a vIGA-AD™ score ≥ 2 :
 - Proportion of subjects who achieved vIGA-AD™ = 0 or 1 at least 1 time during the study
 - [REDACTED]
- The following endpoints will be summarized over subjects in the intent-to-treat (ITT) population:
 - [REDACTED]
 - [REDACTED]
 - [REDACTED]
 - [REDACTED] change and percent change from Baseline in %BSA affected by visit (OC and LOCF).
 - [REDACTED]

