10.5 Interim Analysis and Data Monitoring

An interim analysis will be performed to review safety data after at least 100 pediatric subjects (<18 years of age) have reached 48 weeks of potential active study drug treatment, inclusive of active study drug treatment in one of three parent (i.e., pivotal and maximal use) studies. All summaries will be produced for interim analysis.

The final analysis will be conducted after study completion (i.e., the last subject's last visit) and database lock.

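### The AESI duration summary drops events still ongoing at end of study instead of censoring them, so reported durations run short, most of all for persistent events

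*SAP*

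**What the plan says.** The first study endpoint in the Protocol Synopsis is "Incidence, frequency, and duration of treatment-emergent AEs and SAEs".

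SAP Section 13.2 plans a fuller summary for each AESI type: "Information summarized will include number of events per subject, earliest onset day, duration (in days), causality, grade and seriousness of AESIs, outcome, actions taken", among other items. If a subject has several occurrences, the summary takes the subject's "maximum duration, highest levels of causality and seriousness, maximum grade" and generally the most extreme level of each characteristic. It then adds: "If an AESI was ongoing at end of study (EOS), it will not be included in the duration summary".

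Four other rules bear on this:
- For the Kaplan-Meier figure of time to first AESI, the same section says: "Subjects not experiencing the AESI will be censored at the date of study completion or discontinuation".
- On missing dates: "If the start date or end date is completely missing, duration will not be calculated".
- For events carried over from a parent study, "duration will be computed using the DMVT-505-3103 Visit 1 date as the AE start date".
- SAP Section 10.5 says of the interim: "All summaries will be produced for interim analysis".

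In the visible text of Section 13.2, other TEAEs are tabulated by incidence, and their durations appear only in a listing.

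**The concern.** Leaving out an unresolved event is not neutral. Whether an event is still open at end of study depends on how long it lasts, so the events removed are disproportionately the long ones. The rule also works against the plan's own choice of the subject's maximum. A subject whose longest event is unresolved either disappears from the duration summary or is represented by a shorter, resolved event.

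The interim has the same problem with less follow-up. The exclusion sentence refers only to end of study, but an event open at the data cut has no end date, so no duration is calculated for it.

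What is at stake is the description of tolerability under long, intermittent use. How long these three event types last is a question the study sets out to answer, and the summary would understate the persistent ones most.

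**Working it through.** **Inputs.** From SAP Section 7, Week 49 (Day 344) is labelled End of Study/Follow-up and Week 48 is Day 337. The deletion and subject-maximum rules come from SAP Section 13.2. The documents give no AESI duration, onset pattern or share ongoing, so there is no plan figure to reproduce. Every distribution below is an assumption.

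**Share of events excluded.** Let onset be uniform over Days 1-337, so the time left to Day 344 is uniform between 7 and 343 days (a span of 336). For exponential durations with mean m:

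share excluded = (m / 336) × (e^(−7/m) − e^(−343/m))

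- m = 14: 0.0417 × 0.607 = 2.5%
- m = 60: 0.1786 × (0.890 − 0.003) = 15.8%
- m = 180: 0.5357 × (0.962 − 0.149) = 43.6%

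**Effect on the reported duration.** The table shows simulation results for the same model without dropout. The subject maximum uses zero-truncated Poisson counts averaging 1.3 new events per affected subject.

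| True mean, days | Events excluded | Median, resolved only vs true | Mean subject maximum, reported vs true |
|---|---|---|---|
| 14 | 2.5% | 9.4 vs 9.7 | 15.3 vs 16.0 |
| 30 | 7% | 19 vs 21 | 31 vs 34 |
| 60 | 16% | 34 vs 42 | 53 vs 69 |
| 180 | 44% | 65 vs 125 | 89 vs 205 |

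At 60 days, 12% of affected subjects drop out of the duration summary and 6% are shown with a shorter event. At 180 days the figures are 37% and 12%. With exactly two events per subject, a true mean of 60 days and onset uniform over all 343 days, the true mean maximum is 60 × (1 + 1/2) = 90 days. The rule reports 63.9, and 23% of subjects are shown with a shorter event.

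**Why spread matters.** With onset uniform over T = 343 days and all durations below T, the mean of the resolved events falls short by Var(D) / (T − E[D]). For a mean of 60 days:
- Exponential: 3600 / 283 = 12.7 days. This is approximate, because a few durations exceed T; numerical integration gives 12.4.
- Gamma with shape 4: 900 / 283 = 3.2 days.

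**Sensitivity.**
- Early onset (Days 1-84), exponential: nothing is excluded at 14-30 days. At 60 days 0.7% is excluded (median 41.1 vs 41.6), and at 180 days 19% (94 vs 125).
- Log-normal (log-SD 1), Days 1-337: 15% is excluded at 60 days (31 vs 36) and 41% at 180 days (70 vs 109).
- Gamma (shape 4): the mean is 2% short at 30 days, 5% at 60 days and 24% at 180 days.
- Dropout of 20%: the exclusion at 60 days rises from 16% to 17%.
- Interim, follow-up at the cut uniform over Days 29-344, exponential: 7.5% is excluded at 14 days, 28.5% at 60 days (29 vs 42) and 58% at 180 days (50 vs 125). With follow-up over Days 169-344, 23% is excluded at 60 days.

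**Does censoring repair it?** For exponential durations with onset over 343 days and true means of 30, 60, 120 and 180 days, the true medians are 20.8, 41.6, 83.2 and 124.8 days. Kaplan-Meier gives 20.8, 41.6, 83.2 and 124.9. The resolved-only rule gives 18.9, 34.0, 54.0 and 65.3. Kaplan-Meier also recovers the true median under the log-normal and gamma models.

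**The case against.** The strongest counter-case has five parts.

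1. **Follow-up and the meaning of end of study.** Protocol Section 8.3.2 follows adverse events to resolution or stabilisation, so end dates after Day 344 may exist. Protocol Section 7.8 also defines end of study as the last active subject's follow-up visit. On that reading, some events that resolve after the subject's own Week 49 would stay in. This caveat stands for the size. The SAP's visit table makes Week 49 the likelier reading, and either way the rule turns on status at end of study and censors nothing.

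2. **Size.** No passage supports a mean of 180 days. The simulation draws events independently, so at 180 days about 59% of two-event subjects have overlapping events of the same type. Low-variance durations cut the bias at 60 days to about a quarter of the exponential figure. All of this stands and limits the numbers. It does not change the direction or the growth with event length.

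3. **Transparency.** The SAP states the exclusion openly, the AESI summary includes outcome, and the listings show end dates. Readers can see that unresolved events exist, and table shells, which are not in the documents, may carry a footnote. But an outcome count does not correct a mean or median duration.

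4. **The remedy.** Kaplan-Meier on the first occurrence is a different quantity from the subject maximum. Censoring at withdrawal may be informative: Protocol Section 4.5.1 lists related adverse events as grounds for withdrawal, and no follow-up visit is required after early termination. This stands as a limitation to state in the SAP.

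5. **Rank.** The study is descriptive, and AESI incidence, grade, outcome and time to onset are unaffected. That is why the point should be fixed but does not threaten the study.

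**Conclusion.** The concern holds. The rule deletes events according to their length, no visible passage repairs the duration statistic, and the result is biased short in the only tabulated duration summary for part of a listed endpoint. The direction needs only that durations vary and do not depend on onset day.

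The size is wholly assumed. It is negligible for events lasting a week or two, or starting early. At a true mean of 60 days with onset spread over the study, the mean of resolved events falls short by about 5% (low-variance gamma) to 27% (log-normal). For events lasting around six months the shortfall is roughly 24% to 54%. The documents do not say which of these patterns the three AESIs follow. Confidence is high on direction and necessarily low on size.

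**What to change.** Replace the exclusion sentence in SAP Section 13.2 with wording such as:

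> For each AESI type, duration will be summarised by Kaplan-Meier using each subject's first on-study occurrence. Events ongoing at study completion, discontinuation or the interim data cut will be censored at that date. The median, quartiles and number ongoing will be shown.

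State which date counts as end of study, and note that censoring at withdrawal assumes withdrawal is unrelated to how long the event would have lasted.

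If the subject-maximum table is kept, label it *resolved events only* and print how many subjects were dropped and how many had a longer unresolved event. This label with counts is the minimum repair.

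Summarise carried-over AESIs separately, labelled as time on this study. Restarting the clock at Visit 1 shortens each event's own length but need not bias the summary: under an exponential model with true mean 60 days and parent-study onset uniform over the preceding 56 days, the restarted mean is 60.0. Parent-study onset dates should be used only with left truncation at Visit 1, since pooling them untruncated would give a mean of 84 days.

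The cost is two SAP sentences and one Kaplan-Meier table for each of the three AESIs, with no new data collection. Reported durations will be longer, later recurrences fall outside the first-occurrence estimate, and the median or upper quartile may not be estimable if few events resolve.
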